1.2 Secondary Objectives

1.2.1. To evaluate changes in platelets and in hemoglobin from pre-op to post-op level for patients randomized to receive perioperative TXA versus placebo.

- Study endpoint: changes in platelets and in hemoglobin from pre-op to post-op level, continuous measurement.

1.2.2 To evaluate differences in post-operative daily surgical drain output for patients randomized to receive perioperative TXA versus placebo.

- Study endpoint: postoperative daily surgical drain output, continuous measurement, for the duration of the drain.

1.2.3. To evaluate changes in estimated blood loss (EBL) for patients randomized to receive perioperative TXA versus placebo.

- Study endpoint: estimated blood loss, continuous measurement.

1.2.4. To evaluate the association between the intra-or post-operatively transfused blood volume and estimated blood loss (EBL) for patients randomized to receive perioperative TXA and placebo, respectively.

- Study endpoint: intra- or post-operatively transfused blood volume, continuous measurement, until resumption of chemotherapy; estimated blood loss (EBL), continuous measurement.

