2.2 Rationale

Children, adolescents and young adults undergoing major surgery are frequently exposed to a high risk of perioperative bleeding with concomitant requirement of blood product transfusion. This increases the risk of postoperative adverse outcomes, resulting in longer length of hospital stay and increased morbidity and mortality. The underlying mechanisms that increase the bleeding risk differ depending on the type of surgery performed. Increased fibrinolysis has been implicated as a contributing factor in excessive blood loss in pediatric spinal surgery, adult arthroplasty (TKA) and other major surgeries. Studies utilizing TXA in pediatric orthopedic surgery support its use to reduce perioperative blood loss, drain output and post-operative hematoma. 1,2,11,15

Because of the significant risks and complications associated with blood loss and allogenic transfusions, efforts to identify safe and effective ways of minimizing blood loss perioperatively are crucial. Reducing blood loss and transfusion needs minimizes post-operative complications, hospital stay length, and decreases risk of development of transfusion related complications such as allergic or transfusion reactions, transfusion-related acute lung injury (TRALI), or risk of transmission of blood borne illness^{18,19}.

Maintaining a nearer to normal Hgb and Hct allows the patient to undergo more aggressive physical therapy sooner. Higher postoperative Hgb and Hct levels promote improved wound healing as well. The use of antifibrinolytic drugs will help to improve clinical care and functional outcome of children undergoing limb salvage operations.

The administration of antifibrinolitics, such as TXA and EACA, has been shown to reduce bleeding in various surgeries including cardiac, trauma, hip, and knee arthroplasty, gynecological, and urologic procedures in adolescents and young adults.^{1,2} Since January of 2014 to December of 2017, 39 patients at our institution underwent limb-sparing tumor resections of the proximal tibia or distal femur that met the inclusion criteria for our proposed study. All 39 patients received either an intraoperative or postoperative blood transfusion. The average total blood volume transfused was 19.78 mL/kg with a standard deviation of 11.38 mL/kg. The average number of transfusions received was 2.95 with a standard deviation of 1.83. The average Estimated Blood Loss per Kilogram of Body Weight was 17.84 mL/kg with a standard deviation of 16.28 mL/kg.

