6.2.6 Post-op coags

6.2.7 ROTEM

6.2.8 Management of drain and drain output

- 6.2.8.1. Drain emptied and recorded at discharge from PACU
- 6.2.8.2. Measured and recorded when drainage collection system bag is full and/or every 8 hours.
- 6.2.8.3. Drains will be placed to Hemovac or Somavac collection system. "Wall suction" will not be utilized.
- 6.2.8.4. Daily measurement of drain output will be tabulated (over a 24 and 48-

hour period)

6.2.8.5. Negative pressure wound therapy (if used) “output” will be measured and recorded per routine.

6.2.8.6. Patient to remain on antibiotics while drain is in.

6.2.8.7. Drains will be pulled when output is 75 ml or less per 24- hour period

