6.2.10 Incisional healing

6.2.10.1. Presence or absence of dehiscence

6.2.10.2. Presence or absence of clinically significant hematoma

6.2.11 Functional Assessment

6.2.11.1. All patients enrolled on the study will receive a standard physical therapy evaluation at the same timepoints (with a window of +/- 2 weeks for all):

- weeks post-operatively
- 3 months post-operatively
- 6 months post-operatively

6.2.11.2 Additionally, during each physical therapy evaluation, participants will complete the FMA, PROMIS, and ROM assessment of the lower extremities.

6.2.11.3 See Appendix V.

Please see the table below for more detail and obtain other tests as needed for good patient care.

REQUIRED EVALUATIONS, TESTS, AND OBSERVATIONS

STUDIES TO BE OBTAINED	Pre-Op	In surgery/PACU/ Post-op	End of Study
History	X	with each outpatient visit	X
Physical Exam (Ht, Wt, BSA, VS, BMI)	X	with each outpatient visit	X
Type and screen	X		
CBC with differential, platelets	X	In PACU; daily while inpt; 1 week post-op	X
Urinalysis	X		
ROTEM		X In PACU	
Transfusions (amount in cc)		X	
Drain output (amount in cc)		X, daily until pulled	
Incisional healing (visualization)		X Post-op	X
Estimated Blood Loss		X At conclusion of surgery	
CMP	X	In surgery; daily while inpt; post-op day 3; 1 week post-op	X
Wound f/u		Daily until hospital discharge. At week 1 +/- 4 d for all pts; Every 10-14 days +/- 4 d for "high risk" participants; Every 7-10 days +/- 4 d for wounds undergoing active management of problems; At 6,12 weeks +/- 2 wks. for "low risk" participants; All pts. at 2 & 3 months +/- 3 wks.	X
PT, INR, PTT, fibrinogen	X	PACU; Inpt; 1 week post-op	X
Pregnancy Test*	X		
Physical therapy attendance	X	Inpt, 1, 2, 4 and 6 weeks post op +/- 2 wks; 2 and 3 mos. post op +/- 2 wks	X
Functional Mobility Assessment (FMA)		6 wks., 3 mos. post op +/- 2 wks	X
PROMIS	X	6 wks., 3 mos. post op +/- 2 wks	X
ROM	X	6 wks., 3 mos. post op +/- 2 wks	X

* The St. Jude IRB requires that a female patient of childbearing potential must have a negative pregnancy test as a condition of clinical research eligibility.

Obtain other studies as needed for good patient care. End of study for each participant will be after the 6-month evaluation (+/- 1 month) has been completed.

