11. STATISTICAL CONSIDERATIONS

11.1 Sample Size Consideration and Randomization

This study will be conducted as a randomized, placebo-controlled double-blind trial of the administration of TXA vs. placebo prior to a limb salvage procedure. The primary objective will be to evaluate if TXA will reduce the proportional blood transfusion volume and EBL. The sample size is calculated based on the hypothesis that the TXA administration will reduce the average total volume of red blood cell transfused per kilogram of body weight by 40% relative to the average total volume of red blood cells transfused of the placebo group. Our historical data should be representative of our proposed placebo group, and historically, the average total red blood cell volume transfused per kilogram of body weight is $19.78 \text{ mL/kg} \pm 11.38$. The distribution of the intra-or post-operatively transfused blood volume is normally distributed after $\log(1+x)$ transformation (mean=2.906, sd = 0.507). We use the two-sample t-test with unequal variances to access the primary objective through the $\log(1+x)$ transformation of proportional blood transfusion volume.

We calculate the sample size with the two-sided two-sample t-test with unequal variances for the $\log(1+x)$ transformation proportional blood transfusion volume. Nineteen patients in each group are sufficient to detect a 40% decrease of $\log(1+x)$ transformation of proportional blood transfusion volume (mean=2.435, sd = 0.488) with 0.8 power and type I error 0.05. It can be safely assumed that the number of patients who

do not require blood transfusion is less than 5%. Given the sample size, we do not anticipate the blood transfusion volume will have substantial ties at 0.

Randomization will be performed in the SJCRH Pharmaceutical Services Department by a pharmacist using the randomization program developed by the Department of Biostatistics.²⁶ The drug is clear and will be given IV. The people who would determine the transfusion volume are blinded to the treatment. The randomization is stratified by the variable pre-operative weight that leads to two strata: pre-operative weight > 45.2 kg and pre-operative weight <=45.2 kg, where 45.2 kg is the median of pre-operative weight in the historical control data underwent limb-sparing tumor resections of the proximal tibia or distal femur. The assignment ratio of the TXA group to the placebo group is 1:1.

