11.3 Secondary Objectives

11.3.1. To evaluate changes in platelets and hemoglobin from pre-op to post-op level for patients randomized to receive perioperative TXA versus placebo.

Summary statistics will be provided for the changes in platelet level and decline in hemoglobin from pre-op to post-op level, for both the TXA and placebo group. Two sample t-test or Wilcoxon rank sum test will be used to compare the differences between the two groups. Multiple comparison correction might be used for p-values to address the multiple testing issues due to measurements at multiple time points.

11.3.2. To evaluate differences in post-operative daily surgical drain output for patients randomized to receive perioperative TXA versus placebo.

Summary statistics will be provided for postoperative daily surgical drain output (in milliliters per 24 hour period for the duration of the drain) for each group. The group difference will be compared using two-sample t-test or Wilcoxon rank sum test depending on the distribution of the observed data. Multiple comparison correction might be used for p-values to address the multiple testing issues due to measurements at multiple time points.

11.3.3. To evaluate changes in estimated blood loss (EBL) for patients randomized to receive perioperative TXA versus placebo.

The EBL for pre-op to post-op level, for both the TXA treated group and placebo group will be estimated with a two-sided 95% confidence interval. The EBL of the two groups (TXA vs. Placebo) will be evaluated using a two-sample t-test or Wilcoxon rank sum test depending on the distribution of the observed data.

11.3.4. To evaluate the association between the intra-or post-operatively transfused blood volume and estimated blood loss (EBL) for patients randomized to receive perioperative TXA and placebo, respectively.

Regression model will be used to access the correlation between the log transformed intra-or post-operatively transfused blood volume and EBL.

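### Drain output (in mL) and EBL (unit not stated) are compared without adjustment for body weight, although randomization is stratified by weight; the possible cost is precision, not bias

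*Combined protocol and SAP*

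**What the plan says.** **Drain output.** Section 11.3.2 summarizes it "in milliliters per 24 hour period for the duration of the drain" and then says: "The group difference will be compared using two-sample t-test or Wilcoxon rank sum test depending on the distribution of the observed data". The evaluations table in section 6.2 collects it in cc.

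**EBL.** Objective 1.2.3 reads "Study endpoint: estimated blood loss, continuous measurement", without a unit. Section 11.3.3 adds none: "The EBL of the two groups (TXA vs. Placebo) will be evaluated using a two-sample t-test or Wilcoxon rank sum test". The one historical figure is per kg. Section 2.2 says "The average Estimated Blood Loss per Kilogram of Body Weight was 17.84 mL/kg", with SD 16.28 mL/kg.

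**Weight.** The primary endpoint is transfused volume in mL/kg (1.1.1, 11.2.1). Section 11.1 says "The randomization is stratified by the variable pre-operative weight", cut at the historical median of 45.2 kg. Weight is measured before enrollment (6.1) and again pre-operatively (table in 6.2). No analysis in 11.2 or 11.3 names weight or the stratum as a term. Section 11.4.2 alone mentions covariates, and does not list them.

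**Association of transfusion and EBL.** Objective 1.2.4 and section 11.3.4 give no unit for either variable.

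**The concern.** Eligibility covers everyone under 25 with no lower age limit, and the transfusion rule in 6.2.1.2 provides for patients on both sides of 30 kg, so body size probably varies a good deal. If larger patients bleed and drain more, size adds variance to drain output, and to EBL if that is analysed in mL. That variance has nothing to do with tranexamic acid (TXA). An unadjusted two-sample test leaves it in the error term. With 38 evaluable patients there is little precision to spare, and the variable that would remove this noise is already the stratification factor.

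The missing EBL unit is a separate gap. The analyst could choose mL or mL/kg after seeing the data, on top of the data-dependent choice between t-test and Wilcoxon. Until both scales are fixed, the regression in 11.3.4 has no definite meaning.

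**Working it through.** **1. The plan's own figure (primary endpoint).** Inputs from 11.1: log(1+x) means 2.906 and 2.435, SDs 0.507 and 0.488, two-sided 0.05, unequal variances.

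- Difference = 2.906 − 2.435 = 0.471.
- Standard error at 19 per arm = √((0.507² + 0.488²)/19) = 0.1614.
- Noncentrality = 0.471/0.1614 = 2.92, with about 35.9 df.
- Power is 0.810 at 19 per arm and 0.788 at 18, so 19 per arm reproduces.

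The plan states no power for drain output or EBL.

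**2. Model for the secondary endpoints.** Let loss = weight^b × lognormal residual, with residual log-SD s and log-weight SD w.

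- SD of log mL = √(s² + b²w²).
- SD of log mL/kg = √(s² + (1−b)²w²).
- A 40% reduction is −ln 0.6 = 0.511 on the log scale.
- Power comes from the noncentral t with 36 df and noncentrality 0.511/(SD × √(2/19)).

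**3. Inputs.**

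- EBL: s = √ln(1 + (16.28/17.84)²) = 0.778, from section 2.2, assuming a lognormal shape.
- Drain: s = 0.5 is an assumption; the documents contain no drain data.
- Weight: w = 0.3 to 0.5 is an assumption; only the median is given. Around 45.2 kg, w = 0.3 puts the central 95% at 45.2 × exp(±1.96 × 0.3) = 25 to 81 kg. At w = 0.5 it is 17 to 120 kg, so 0.5 is a wide upper case.

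**4. Unadjusted comparison in mL, full proportionality (b = 1).**

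| Endpoint | w | SD of log mL | Added variance | Power |
|---|---|---|---|---|
| Drain, s = 0.5 | 0 (reference) | 0.500 | – | 0.87 |
| | 0.3 | 0.583 | 36% | 0.75 |
| | 0.4 | 0.640 | 64% | 0.67 |
| | 0.5 | 0.707 | 100% | 0.58 |
| EBL, s = 0.778 | 0 (reference) | 0.778 | – | 0.50 |
| | 0.3 | 0.834 | 15% | 0.45 |
| | 0.4 | 0.875 | 26% | 0.42 |
| | 0.5 | 0.925 | 41% | 0.38 |

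**5. Other exponents (drain, w = 0.4).**

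| b | mL: SD, power | mL/kg: SD, power |
|---|---|---|
| 1 | 0.640, 0.67 | 0.500, 0.87 |
| 0.5 | 0.539, 0.81 | 0.539, 0.81 |
| 0 | 0.500, 0.87 | 0.640, 0.67 |

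The two scales tie at b = 0.5. Below that, dividing by weight is the worse choice.

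**6. Weight-adjusted analysis.** In simulation (2,000 runs per setting, 19 per arm, allocation balanced within weight halves, weight CV 0.3 to 0.5), a log-scale linear model with log weight kept power at about 0.85 to 0.87 for drain output and 0.48 to 0.52 for EBL, for b = 0, 0.5 and 1. The closed form in steps 4 and 5 ignores the stratified allocation, so simulated unadjusted figures differ somewhat. With a log-weight SD of 0.3 to 0.4, the raw-mL drain power was 0.72 to 0.65 at b = 1; at 0.4, the mL/kg power was 0.76 at b = 0. The ordering is the same.

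**7. Stratum only.** If log weight is normal and split at its median, the within-half variance is 1 − 2/π = 0.363 of the total. For drain output at b = 1, the adjusted SD is √(0.25 + 0.363 × 0.09) = 0.532 at w = 0.3 and √(0.25 + 0.363 × 0.25) = 0.584 at w = 0.5. Power is about 0.82 and 0.75, so the stratum recovers only part of the loss.

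**8. Why not log(1+x) of mL/kg.** At 75 mL per day and 45.2 kg, x = 75/45.2 = 1.66. A 40% reduction is then ln(2.66) − ln(2.00) = 0.29, against 0.51 on the plain log scale. The added 1 shrinks the effect when x is small.

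**The case against.** **EBL may already be per kg.** The only EBL figure in the documents is in mL/kg. The sentence on the primary aim in 11.1 places the word proportional before transfusion volume and EBL together, which can be read as covering both. This stands. A reader might infer that EBL is compared in raw mL, but the documents do not show it. What they show is a missing unit and no weight term.

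**The power loss is conditional.** A reader might infer that analysing mL lowers power as such. It does so only to the extent that loss rises with weight, and the documents give no such relation, no weight SD and no drain data. This also stands.

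**The mL unit suits drains.** Output is measured in cc, and the removal criterion is in absolute volume: "Drains will be pulled when output is 75 ml or less per 24- hour period". Reporting in mL is therefore reasonable. That is a reason to keep mL in the tables, not to leave weight out of the model.

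**No validity problem.** Allocation is 1:1 and stratified at 45.2 kg, so body size does not bias the comparison. These are secondary endpoints with no stated power. This stands and limits the point to precision and pre-specification.

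**Objective 1.2.4.** A reader might infer that its regression is partly a body-size correlation. That presumes units which neither 1.2.4 nor 11.3.4 gives. With both variables in mL, shared body size could inflate the association. With one in mL/kg and loss per kg independent of weight, weight noise would attenuate it. With both in mL/kg, the shared denominator matters. Only the lack of a stated scale is established.

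**Conclusion.** The point holds as one of precision and pre-specification. Drain output is compared in mL, and EBL in an unstated unit, by unadjusted tests that ignore the stratification variable. The loss for drain output runs from none, if output does not depend on weight, to a fall from 0.87 to between 0.75 and 0.58 under full proportionality. For EBL, if it is analysed in mL, the corresponding fall is from 0.50 to between 0.45 and 0.38. These figures rest on 19 per arm, a true 40% reduction, lognormal outcomes, an assumed log-weight SD of 0.3 to 0.5 and, for drain output, an assumed residual log-SD of 0.5.

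Two tempting conclusions do not follow. Switching to mL/kg is not in itself the remedy, because it loses power when output is far from proportional to weight. Nor is the trial's main result in question: the primary endpoint is already mL/kg, and the 38 evaluable patients were sized on it alone.

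**What to change.** - **11.3.2 and 11.3.3:** compare the arms by a linear model on the log scale with treatment and log pre-operative weight. Add a small offset only if zeros occur. The weight stratum is the minimum alternative. With log weight in the model and no offset, log mL and log mL/kg give the same treatment estimate and p-value, because dividing by weight only shifts the weight coefficient by one. The choice of scale then no longer affects the test.
- **1.2.3 and 11.3.3:** state the unit of EBL.
- **Tables:** report drain output and EBL descriptively in both mL and mL/kg.
- **1.2.4 and 11.3.4:** state the scale of transfused volume and of EBL, and include log weight as a covariate.

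The cost is SAP wording, best settled before unblinding. Weight is already collected, so no new data or patients are needed.

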11.4 Exploratory Objectives

11.4.1. To evaluate differences in functional outcomes post-operatively for patients randomized to receive perioperative TXA versus placebo.

Summary statistics will be provided for postoperative functional assessment scores (at each physical therapy session and at timepoints 6, 12, and 24 weeks) for each group. The group difference will be compared using two-sample t-test or Wilcoxon rank sum test, depending on the distribution of the observed data. Multiple comparison correction might be used for p-values to address the multiple testing issues due to measurements at multiple time points. We will calculate the missing proportions of the functional outcomes at every follow-up.

11.4.2. To explore if significant correlations are observed between parameters reported with rotational thromboelastometry (ROTEM®) and EBL and transfusion requirements in pediatric and young adult patients undergoing limb salvage procedure who are randomized to perioperative TXA versus placebo.

Multiple regression model is used to analyze the association between each measurement of rotational thromboelastometry (ROTEM®) and EBL and transfusion requirements while accounting for possible covariates. Multiple comparison correction might be used for p-values to address the multiple testing issues due to multiple measurements of ROTEM. Multivariate regression model may be used to study the associations between multiple measurements of ROTEM and EBL and transfusion requirements jointly. We will calculate the missing proportions of ROTEM at every follow-up.

11.4.3. To evaluate differences in the prevalence and management of wound complications such as superficial or periprosthetic infections, wound dehiscence, contact dermatitis, post-operative hematomas, or any other clinically significant wound complication between patients randomized to receive perioperative TXA versus placebo.

The proportions of observed wound complications and proportions of observed interventions will be estimated for both the TXA group and placebo group with 95% confidence intervals and compared between these two groups using Fisher's Exact Test. We will calculate the missing proportions of wound complications at

every follow-up. Multiple comparison correction might be used for p-values to address the multiple testing issues due to measurements at multiple time points.

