Patient-Reported Outcomes Measurement Information System (PROMIS) is a patient-reported outcome tool created by the National Institutes of Health (NIH), to establish a means of systematic outcome reporting for all patients across the health care spectrum.²¹ Due to its efficiency, reliability, and applicability to all patient types, the PROMIS continues to grow in popularity in many fields of medicine, including pediatrics, oncology, and orthopedics.²²⁻²⁵ It has shown good validity in both adult and pediatric populations, and is available in pediatric (ages 8-17), adult (ages 18 and older), and parent proxy (ages 5-17, or those unable to complete form independently) versions. The physical function domain of the PROMIS is intended to capture a patient's self-reported ability to perform daily activities, self-care, and athletic activities, and are subdivided into the areas of mobility and upper extremity. Additional domains utilized for this study include strength impact and pain interference. PROMIS forms will be provided to all patients enrolled on this study at the time of their functional assessment with adequate, allotted time for completion of questionnaires, and collection of forms at the end of assessment appointment.

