APPENDIX VI: RELATION OF STUDY ENDPOINTS TO PROTOCOL OBJECTIVES

Item	Pre-OP	PACU	1-6 d Post-OP	1 wk. Post-OP	2 wks. Post-OP	4 wks. Post-OP	6 wks. Post-OP	2 mos. Post-OP	3 mos. Post-OP	6 mos. Post-OP
Objectives 1.1.1 & 1.2.3 & 1.3.2: Amount of Blood transfused/ placebo arm		X	X							
Objectives 1.1.1 & 1.2.3 & 1.3.2: Amount of Blood transfused/ TXA- treatment arm		X	X							
Objectives 1.2.1: Platelet changes/placebo arm	X	X	X	X						
Objective 1.2.1: Platelet changes/TXA-treatment arm	X	X	X	X						
Objective 1.2.1: Hemoglobin changes/ placebo arm	X	X	X	X						
Objective 1.2.1: Hemoglobin changes/ TXA-treatment arm	X	X	X	X						
Objective 1.2.2: Drain output/placebo arm		X	X	X						
Objective 1.2.2: Drain output/ TXA-treatment arm		X	X	X						
Objectives 1.2.3 & 1.2.4 & 1.3.2: EBL/placebo arm (includes sponge counts + other measures during surgery)			X							
Objectives 1.2.3 & 1.2.4 & 1.3.2: EBL/TXA treatment arm (includes sponge counts + other measures during surgery)			X							
Physical Therapy Attendance (could relate to obj 1.3.1)	X		X	X	X	X	X	X	X	X
Objective 1.3.1: FMA							X		X	X
Objective 1.3.1: PROMIS	X						X		X	X
Objective 1.3.2 ROTEM		X								
Objective 1.3.3 Wound f/u placebo arm (as needed)		X	X	X	X	X	X	X	X	X

Objective 1.3.3 Wound f/u TXA-treatment arm (as needed)		X								
---	--	----------	----------	----------	----------	----------	----------	----------	----------	----------

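### PROMIS is collected before surgery for Objective 1.3.1, but Section 11.4.1 compares post-operative scores without using it: a valid analysis that gives up some precision on an exploratory endpoint.

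*Combined protocol and SAP*

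**What the plan says.** Objective 1.3.1 names two functional endpoints, FMA and PROMIS. The evaluation table in Section 6.2 and the schedule in Appendix I place PROMIS before surgery and at 6 weeks, 3 months and 6 months. Appendix VI has a row labelled "Objective 1.3.1: PROMIS" with a mark in the pre-operative column, so the plan itself assigns that baseline to this objective. FMA has no pre-operative assessment in any of the three tables.

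For the analysis, Section 11.4.1 says: "Summary statistics will be provided for postoperative functional assessment scores". Arms are then compared by a two-sample t-test, or a rank-sum test if the distribution calls for it. The section names no change score, baseline covariate or repeated-measures model, and no other section supplies one for these outcomes. Elsewhere the plan does use such information: platelets and hemoglobin are analysed as changes from the pre-operative level (11.3.1), and the ROTEM regression allows for covariates (11.4.2).

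Randomization is stratified by pre-operative weight at 45.2 kg (11.1), and the stratum does not appear in 11.4.1 either. Appendix V adds that PROMIS "is available in pediatric (ages 8-17), adult (ages 18 and older), and parent proxy" versions.

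**The concern.** A pre-operative score is often the best single predictor of the same score later. With about 19 patients per arm, an unadjusted comparison carries all of the between-patient spread in pre-operative function in its standard error. If the baseline correlates with follow-up, putting it in the model narrows the confidence interval without another patient or visit.

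Section 11.2.2 projects 39 patients over 48 months at one site, so more precision cannot readily come from more accrual. What is at stake is how informative the PROMIS comparison will be. The validity of that comparison is not in question, and neither is the primary result.

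**Working it through.** **Inputs from the documents.** 1:1 allocation ("The assignment ratio of the TXA group to the placebo group is 1:1"), 19 per arm, 38 evaluable (11.1). For the primary endpoint on the log(1+x) scale: placebo "mean=2.906, sd = 0.507"; TXA "mean=2.435, sd = 0.488) with 0.8 power and type I error 0.05". No variance, effect size or correlation is given for PROMIS.

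**Step 1: the plan's own figure.** The plan states a sample size only for the primary endpoint: "Nineteen patients in each group are sufficient to detect a 40% decrease".
- Difference: 2.906 − 2.435 = 0.471.
- Averaged SD: √[(0.507² + 0.488²)/2] = 0.4976.
- Standardized difference: 0.471/0.4976 = 0.947.
- The normal approximation gives 18 per arm. The noncentral t gives power of 78.8% at 18 and 81.0% at 19, with pooled or Welch degrees of freedom.

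So 19 per arm reproduces. This also fixes N = 38 for what follows.

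**Step 2: unadjusted PROMIS comparison.** With 19 per arm and two-sided alpha 0.05, the difference detectable with 80% power is 0.93 SD.

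**Step 3: ANCOVA on the pre-operative score.** Let ρ be the correlation between pre- and post-operative scores (assumed). Relative to the unadjusted comparison, the variance factor is

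(1 − ρ²) × [1 + 1/(N − 4)] = (1 − ρ²) × (1 + 1/34) = (1 − ρ²) × 1.029,

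with 35 error degrees of freedom. The second term is the small-sample price of estimating the slope.

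| ρ (assumed) | Variance factor | Simulated factor | Detectable difference, 80% power | Power at 0.93 SD | Equivalent unadjusted N (38/factor) |
|---|---|---|---|---|---|
| 0 | 1.029 | 1.03 | 0.95 SD | 79% | 36.9 |
| 0.3 | 0.937 | 0.93 | 0.91 SD | 82% | 40.6 |
| 0.5 | 0.772 | 0.77 | 0.82 SD | 89% | 49.2 |
| 0.7 | 0.525 | 0.52 | 0.68 SD | 97% | 72.4 |

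The simulated factors come from 20,000 trials per correlation.

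**Step 4: break-even.** Setting (1 − ρ²) × 1.029 = 1 gives ρ² = 1 − 1/1.0294 = 0.0286, so |ρ| is about 0.17. Below that, adjustment costs a little precision.

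**Step 5: cost of further covariates.** A simulation of a larger model (arm, baseline, weight stratum and two indicators for PROMIS version) gave factors of 1.10, 1.00, 0.82 and 0.56 at ρ = 0, 0.3, 0.5 and 0.7. It assumed a 60/25/15 split of versions, balanced strata, and no prognostic value in version or stratum. Extra terms that predict nothing use up part of the gain, and at ρ = 0.3 all of it.

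**Step 6: why not a change score.** Its variance factor is 2(1 − ρ): 1.4, 1.0 and 0.6 at ρ = 0.3, 0.5 and 0.7. That is worse than no adjustment below 0.5, and worse than ANCOVA at all three values.

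**The case against.** The strongest reply is that nothing here is an error. Under 1:1 randomization the unadjusted test is unbiased and keeps its type I error; chance baseline differences are already reflected in its standard error. The analysis also matches the objective, which asks about post-operative function. The objective is exploratory and carries no sample-size claim. The correlation is unknown, and because the baseline precedes a major limb resection, a low value cannot be excluded. All of this stands, and it limits the point to efficiency.

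Four stronger readings are tempting, and the documents do not support them:
- *That the gain is free, or equals ρ² (9%, 25%, 49%).* Those are large-sample values. At 38 patients the reductions are about 6%, 23% and 48% for baseline alone, less with non-prognostic covariates added, and slightly negative near ρ = 0.
- *That ROM is equally affected.* ROM is measured before surgery, but neither Objective 1.3.1 nor Appendix VI names it. Appendix V also allows the operated limb to go unmeasured under range-of-motion precautions.
- *That PROMIS versions are pooled.* Appendix V says which versions exist; Section 11.4.1 is silent on how they are combined. Silence is not a statement of pooling.
- *That chance imbalance invalidates the comparison.* It does not, for the reason above.

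One practical objection also stands: PROMIS is not among the pre-study evaluations required in Section 6.1, so some baselines may be missing, and a plain ANCOVA would drop those patients.

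What survives is that the plan collects a baseline for this objective and does not use it, when the expected cost of using it alone is at most about 3% in variance and the gain at moderate correlation is several times larger.

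**Conclusion.** The point holds for PROMIS as a loss of precision. Adjusting for the pre-operative score alone would reduce the variance of the arm difference by about 6%, 23% or 48% at ρ = 0.3, 0.5 or 0.7, against an increase of about 3% if ρ is near zero.

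These figures assume approximately normal scores, a linear relation, and 38 patients with both a baseline and a follow-up score; missing data would shrink the numbers. The correlations are assumptions. FMA cannot benefit, since it has no baseline.

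Severity is low: one of two named endpoints in one exploratory objective. The primary endpoint, its sample size and its conclusion are unaffected.

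**What to change.** In Section 11.4.1, before unblinding:
- Compare PROMIS between arms at 6 weeks, 3 months and 6 months by ANCOVA, or by one mixed model over the three visits, with arm, pre-operative PROMIS score and the randomization weight stratum. The planned unadjusted test can stay as a sensitivity analysis.
- Keep patients with a missing baseline by a simple pre-specified method, for example replacing the missing value by the overall pre-operative mean, calculated without regard to arm.
- Use the same PROMIS version at baseline and follow-up where possible, and state how a change of version is handled. Add version as a covariate only if it is expected to be prognostic.
- State whether ROM is analysed under this section. If so, apply the same model where the joint was measured.
- Do not substitute a simple change score.

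The cost is wording only. The pre-operative PROMIS is already scheduled, and no added visit, test or patient is needed.
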